Does Adding a Tailored Cognitive Behavioral Therapy (CBT) Mobile Skills App mediate
Higher Rates of Depression Recovery, Adjustment, and Quality of Life in OEF/OIF
Veterans Compared to Standard CBT?

NCT 04002063

PI: [name] [name]

December 19, 2018

Study Protocol

Recruitment: In addition to the referrals and self-referrals made from the above locations, eligible patients will be identified by reviewing CPRS records. These chart reviews include patients receiving active clinical care and meet our inclusion criteria i.e., has depressive symptoms but are not engaged in therapy.

For patients that we have reviewed through CPRS via a waiver and who received an encrypted email from the Veteran's identified therapist of notification and Veteran permission to call, we will make our first contact by phone. For all other recruitment methods, we will send a letter requesting that they contact us by phone if they so desire. Patients who notify the research staff by phone of their interest, will then be contacted by the research staff about coming in for an evaluation and considering signing the informed consent and the HIPAA authorization. During the initial phone call, following a thorough explanation of the study to the Veteran who has agreed to be contacted, verbal informed consent for a short eligibility survey will be obtained. The eligibility survey will contain the PHQ-9 and Scale of Suicidal Ideation (SOSI) on the phone to establish preliminary eligibility. IRB approval will be attained to perform eligibility ratings prior to written consent.

If preliminarily eligible, Veterans will be invited to come for an in-person visit to sign the informed consent and the HIPAA authorization and complete the full baseline assessment in person. A Suicide Risk Assessment Protocol will be used for telephone interviews. See Human Subjects. Specific elements of the protocol included further evaluation if Question # 9 of the PHQ-9 is "several days, more than half the days or nearly every day" or if the Scale of Suicidal Ideation items two or four (wish to die or desire to make an active suicide attempt are moderate to strong). Specifically, the evaluator must determine how serious the threat is. If the risk is moderate or high, i.e., there is a moderate to high risk of potential harm to the participant, the participant will be placed on hold briefly, and the Veterans Crisis Line will be called and the participant will be transferred to the Veterans Crisis Line Responder. The phone evaluator will be prepared to tell the emergency responder the participant's name, location (i.e., physical address), phone number, last 4 of SSN, and relevant clinical information (e.g., suicide risk level, who the participant is talking with about these thoughts). The evaluator will document this in CPRS.

In addition to the specific suicide protocol we have added, we will: 1) exclude all Veterans who are listed as high suicide risk in CPRS; 2) will train study personnel about methods for handling endorsement of suicide risk during phone screens; 3) clinicians will be available at all times to manage such situations (this will also include the PI, [name], and [name]); and 4) the VA has on-site suicide prevention coordinators who will manage a transfer from study staff for endorsement of suicide risk. The standard of practice at the VA includes a phone evaluation for outpatient services. Our initial research evaluation offers no additional risk than this standard evaluation. Finally, the literature supports the feasibility and safety of telephone screening of depressed individuals with potential suicidal ideation^{5,6,78}.

Informed Consent Procedure: Participants will sign an informed consent prior to initiation of the study baseline study procedure. Initial assessments will cover key demographic, diagnostic, clinical, psychopathologic assessments (See Table 8). Informed consent will be obtained during an in-person interview with the subject and it will be documented on a VAPHS or VA Philadelphia consent form.

Assessments will be completed via paper and pencil. Once participants complete all T1 assessments, they will be randomly assigned to either 1) CBT-D as usual or 2) CBT-D+. The CBT MobileWork-V app documentation will be provided and downloaded on their phone. In addition to an in-person demonstration, we are developing a YouTube video detailing the use of and clear demonstrations about how the app works, its contents, how information is entered, etc.

We have identified a cadre of five CBT certified therapists at each of the Pittsburgh and Philadelphia VA's who are willing to participate with us and have training in VA CBT-D. All therapists will receive comprehensive training on the protocol procedures and a protocol

manual. All of the therapists will receive an in-person training on the app as well as a manual with every screen shot present in the app. They will identify the most appropriate individualized skills practice at the end of each therapy session.

We will facilitate the patient's appointment with the study therapist at the time of randomization. All patient participants will receive reimbursement for their participation (\$30 for T1, \$35 for T2, and \$50 for T3).

Description of Usual Care and Experimental Conditions

Usual Care Condition: After completion of the baseline assessment, study participants will have an appointment set up to meet with one of the VA-trained/certified CBT therapists who will explain how the CBT program will be carried out. CBT-D includes twelve, once weekly, 50-minute sessions (per the VA-specified manual) over a period of up to 20 weeks. There will be a leeway of 8 weeks to complete all sessions (to allow for vacations, illness, etc.). All subjects will have the same therapist throughout. All therapists will complete an Assignment Compliance Rating Scale⁶⁵ following each session, referencing the patient's adherence to last session's HW and additional skills practice.

Experimental Condition: Participants in the experimental condition will have identical therapy procedures as the CBT-D as usual condition (see 3.6.1). They will have access to CBT MobileWork-V throughout the entire study and be instructed to use their study ID as their username and will be given a numeric password. Thus, there will be no identification of the participant through PHI. We will also instruct them to avoid personal identification of themselves or their family members in the smartphone app.

For those that are randomized to the app, we will guide them to a YouTube video detailing clear demonstrations about how the app works, its contents, how information is entered, etc. A user manual will be generated and individualized training on all aspects of CBT will occur for patient and therapists who access or need to assign HW based upon contents of the app CBTMobileWork-V. They will be instructed to use CBT MobileWork-V as the primary method of CBT skills practice.

When the patient opens CBT MobileWork-V, he/she will be prompted to complete a VAS rating from "I feel the worst I have ever felt" to "I feel the best I have ever felt."⁷⁴ This procedure will be repeated when they close the app. The patient will identify the location of the HW and locate it in the pull-down menu. The smartphone application will have consecutive screens that ask the patient to comment on specific areas, i.e. if the patient is doing a dysfunctional thought record it will begin by asking them to describe the situation and why it was upsetting. Thus, the HW assignments are not merely forms, but series of questions that ascertain the crucial HW responses. Patients can then save it in the CBT Toolbox for future reference.

If, during the course of the study therapy, a patient is found to have symptoms that "cannot wait to be treated," therapists will intervene, within the scope of safe therapeutic treatment, e.g. an emergency contact will be set up by phone or in person (and per the intervention manual). Patients with high risk or severe symptoms will be instructed to report symptoms to their therapist in a timely manner.

All assignments cannot be directly completed on the smartphone application. These assignments will be documented on the Assignment Compliance Rating Scale (ACRS) for both the Experimental and Treatment as Usual conditions. Especially in the beginning of therapy, when behavioral activation is required, HW may include graded physical activity. The smartphone application may record the activity, evaluate how the activity affected their mood, or to get ideas for physical activity from My CBT Library.

Statistical Analysis

Analysis Strategy: This study is a two-group, two-site randomized controlled trial. Primary effects of interest are greater CBT understanding and skills acquisition (Primary Aim 1) and lower levels of depression symptoms (Primary Aims 2a and 2b) in the CBT-D+ group compared to CBT-D alone. Secondary effects are lower comorbid diagnosis symptoms (i.e., lower psychological adjustment and reintegration problems, greater functional capacity, and quality of life, and lower levels of anger, PTSD, and anxiety (see table 8).

Independent variables: Randomized treatment group assignment (CBT-D+ versus CBT-D alone).

Dependent Variables: The primary outcomes on which the analysis is powered are CBT understanding and skills acquisition assessed by patient and therapist SoCT and depressive symptoms assessed by PHQ-9.

Sample Size Justification: The proposed sample size of 268 randomized (134 per group) was estimated based on the expected effect sizes to test hypotheses for the primary aims (Hypotheses 1 and 2[a,b]); adjustment of the testwise significance level to .01 for CBT understanding and skill acquisition (as measured by patient and therapist SoCT total scores) (Primary Aim 1) and depressive symptoms (measured by PHQ-9) (Primary Aims 2a and 2b) to limit inflation of type 1 error due multiple testing of hypotheses at 12-weeks post-therapy initiation and 6-months post-therapy; and anticipated attrition at 6-months post-therapy⁷ recommend clinically meaningful effect sizes of 0.50 (in terms of a standardized mean difference, d) when comparing alternative treatments in comparative psychotherapy research. When using the patient and therapist SoCT total scores to measure patient's CBT understanding and skill acquisition, standard deviations (SD) of ~0.72 and ~0.80 have been reported post-therapy by patients and therapists, respectively⁹³. Given these results, clinically meaningful effects of at least $d=0.50$ (or at least 0.36-point and 0.40-point differences in treatment group means assuming SDs of ~0.72 and ~0.80 for SoCT total scores from patients and therapists, respectively) may be detected with 0.80 power with 192 total (96 per group) when comparing mean SoCT total scores from patients and therapists between treatment groups based on linear contrasts from linear mixed model at testwise significance level of .01 (Hypothesis 1).

Regarding Primary Aims 2a and 2b, standard deviations on the order of ~4.0 have been reported for PHQ-9 total scores post-therapy⁸. With minimum group sizes of 96 (192 total), we would have .80 power to detect clinically meaningful differences as small as $d=0.50$ (or at least a 2.0-point difference in treatment group means assuming a SD of 4.00) when comparing mean depressive symptoms (as measured the PHQ-9 total scores) between treatment groups at 12-weeks post-therapy initiation (Hypothesis 2a) and at 6-months post-therapy (Hypothesis 2b) at testwise level of significance of .01.

Although efforts will be made to retain participants through 6-months post-therapy, some attrition may occur. Research in CBT for depressive symptoms and the use of technology/apps to enhance treatment effects support at most 20% attrition at 12-weeks post-therapy initiation⁹ and an additional 8% attrition at 6-months post-therapy¹⁰ for an overall attrition rate of 28% at 6-months post-therapy. To ensure an adequate number of participants with full follow-up, we plan to enroll 134 per group (268 total), to conservatively adjust for overall attrition of 28% at 6-months post-therapy.

Data Analysis: Data will be analyzed using SAS⁹⁴ to conduct exploratory data analyses, missing data estimation, and repeated measures modeling for Primary Aims 1, 2a and 2b and Secondary Aim 2. MPlus⁹⁵ will be used for mediational analyses of Secondary Aim 1. While directional hypotheses have been posited, the level of statistical significance will be set conservatively at .01 to limit type 1 error inflation due to hypothesis testing at multiple outcomes and at multiple time points. Confidence intervals for point estimates will be computed at 99%.

Preliminary Analyses: Exploratory analyses will first be performed involving data description and screening for anomalies (e.g., outliers, nonnormality, missing data) with these results being used to 1) describe univariate/bivariate data distributions; 2) identify treatment

group imbalances and associations between dependent variables and suspected covariates/confounders; 3) evaluate the amount and patterns of missing data; and 4) check for violations of assumptions for the planned analysis strategies. If assumptions are violated, data transformations or more statistically robust procedures will be considered as appropriate. Covariates/confounders will be included in analyses secondarily and their impact on the results will be evaluated. The randomness of missing data will be investigated using available information on participant characteristics to help discern patterns in the missing data, identify possible missing data mechanisms, and inform the strategies used to handle missing data. If data are missing completely at random or missing at random, the likelihood based estimation procedures to be used will produce unbiased estimates while allowing us to retain observations with missing values on the dependent variables. If needed, multiple imputation (e.g., Markov Chain Monte Carlo with the number of imputations based on the extent of missing data) will be used to impute missing values on covariates. If nonrandom missingness is suspected, we will use selection or pattern mixture modeling to explore the sensitivity of results to assumed missing data patterns.

Analysis Plan for Primary Aim 1: An "intent-to-treat" (ITT) approach will first be used for efficacy analyses of CBT-D+ compared to CBT-D alone. All participants will be analyzed "as randomized", regardless of protocol adherence, treatment received, withdrawal or protocol deviations. Although recommended for efficacy analyses in RCTs, the sensitivity of the results assuming ITT will also be explored using data collected on the participant's adherence to their assigned treatment group using an instrumental variables approach ⁹⁶as well as ad hoc approaches (e.g., per protocol, amount of treatment received).

The primary outcome variable for this aim is CBT understanding and skill acquisition (as measured by the patient and therapist SoCT total scores) assessed at baseline prior to randomization, completion of the acute phase of treatment (12-weeks post-therapy initiation), and 6-months post-treatment. Linear mixed modeling will be used to examine the overall efficacy of CBT-D+ on patient's CBT understanding and skill acquisition from both the patient's and therapist's perspectives over time. When fitting models to each of these dependent variables, time will be treated as fixed, categorical, repeated within-subject factor, while randomized treatment assignment (CBT-D+ vs. CBT-D alone) will be a fixed, categorical, between-subject factor, with interactions between time and randomized treatment assignment. In addition to the baseline value of the SoCT total scores, time-invariant and/or time-dependent covariates may be included to adjust for treatment group imbalances or variables related to the dependent variables of interest. In keeping with linear mixed modeling, random effects for participants will be included as well as possible random site effects. Standard fit indices will be used to identify the best-fitting variance-covariance structure for the repeated measures. We will also consider time as a continuous variable through the use of mixed effect regression models to accommodate individual deviations from the average trends. F-tests will be used to test the main effects and interactions included in the model. For each model, residual analyses will be used to identify possible model misspecification, outliers and influential cases. Sensitivity analyses will be performed to discern the impact of influential observations on results. To test hypotheses for Primary Aim 1 (Hypothesis 1) by formulating linear combinations of the model parameters from the fitted model, group comparisons between CBT-D+ and CBT-D alone will be performed at a) 12-weeks post-therapy initiation and b) 6-months post-therapy. Effect size indices with confidence intervals will be reported for the overall effect of the addition of CBT MobileWork V to CBT-D and at each time point of interest. Lastly, we will also explore possible modification of the treatment effect by participant characteristics (e.g., sex, age, etc.).

Analysis Plan for Aims 2a and 2b: For the most part, we will use a similar repeated measures approach as outlined for Aim 1 to fit linear mixed models for the primary distal outcome of depressive symptoms at baseline prior to randomization, 12-weeks post-therapy initiation, and 6-months post-treatment. Linear mixed modeling will be used to examine the overall efficacy of

CBT-D+ relative to CBT-D alone on patient's depressive symptoms (as measured by total scores on the PHQ-9) over time. To test aim-specific hypotheses and estimate the corresponding effect sizes, group comparisons between treatment groups will be performed at a) 12-weeks post-therapy initiation (Hypothesis 2a) and b) 6-months post-therapy (Hypothesis 2b). To examine the durability of the effect of CBT-D+, we will also examine changes in depressive symptoms from a) 12-weeks post-therapy initiation to 6-months post-therapy and b) baseline to 6-months post-therapy.

Analysis Plan for Secondary Aim 1: We will explore CBT skills practice (as measured by the Assignment Compliance Rating Scale and the number of homework assignments completed) and acquisition of additional CBT skills (as measured by the SoCT P & T) as intermediate outcomes that may mediate the effect of the addition of CBT MobileWork-V to CBT-D on the distal outcome of depressive symptoms. Initially, we will fit simple mediational applying the change score method and estimate whether the effect of the addition of CBT MobileWork-V (predictor) on changes in depressive symptoms (outcome) is mediated through changes in the suspected mediators of CBT skills practice and acquisition of additional CBT skills. In addition to the chi-square goodness of fit statistic, standard summary fit indices (e.g., root mean square error of approximation, comparative fit index) will be used to assess the fit of the mediational model to the data, followed by model assessment via residual analyses. Total, indirect and direct effects will be estimated and reported with confidence intervals. If nonnormality is encountered, robust estimation methods (e.g., robust maximum likelihood estimation) will be used, or resampling approaches with the percentile bootstrap will be applied. Depending on the results from simple mediational modeling, we may also combine mediators and incorporate additional potential mediating/moderating variables (e.g., the number of CBT therapy sessions completed) into a multiple-mediator model to develop a more comprehensive picture of the possible pathways. Additionally, we will explore CBT skills practice and acquisition of additional CBT skills as mediational processes on depressive symptoms as an outcome process using parallel process latent growth curve modeling, where the mediational process is modeled by relating the randomized treatment group assignment (CBT-D+ vs. CBT-D) and the latent growth factors of the two parallel processes.

Analysis Plan for Secondary Aim 2: Using a similar analysis approach as described for Aim 1, we will use linear mixed modeling (or generalized linear mixed modeling, if dependent variables are binary with binomial errors) to explore the effect of CBT-D+ compared to CBT-D alone on the more secondary outcomes of OEF/OIF comorbid disorders/issues, including work and home functioning (assessed by the Military to Civilian Questionnaire and Disability Assessment Schedule), quality of life (assessed by the WHO-QOL), anxiety (assessed by the GAD-7), anger (assessed by the Dimensions of Anger Reactions), and lastly PTSD (based on the PTSD Checklist) following 12 weeks of weekly CBT-D sessions and at 6-months post-therapy. For these explorations, the estimation of effect sizes (with confidence intervals) will be emphasized to summarize short- and long-term effects of CBT-D+, compared to CBT-D, on work and home functioning, quality of life, anxiety, anger and PTSD at 12-weeks post-therapy initiation and 6-months post-therapy, respectively.

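### Ten therapists share the patients and rate one primary outcome, but the primary models name no therapist term: a cheap addition that gains modest precision and guards against therapist assignment that leans by arm

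*Combined protocol and SAP*

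**What the plan says.** The therapist paragraphs of the Study Protocol identify "a cadre of five CBT certified therapists at each of the Pittsburgh and Philadelphia" sites. Under Usual Care Condition, "All subjects will have the same therapist throughout". Therapist SoCT is a primary outcome alongside patient SoCT and PHQ-9 (Dependent Variables; Analysis Plan for Primary Aim 1).

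For the primary model the SAP states that "random effects for participants will be included as well as possible random site effects". Further covariates are optional and therapist is not among those named. Effect modification is planned for participant characteristics only. The Analysis Plan for Aims 2a and 2b adopts largely the same approach for PHQ-9.

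Two points are left open:

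- **Whether each therapist treats both arms.** It is implied: "All of the therapists will receive an in-person training on the app", and app participants "will have identical therapy procedures as the CBT-D as usual condition". No section says so outright. The therapist appointment is arranged at randomization, and no rule spreads therapists over arms.
- **Who gives the baseline therapist SoCT score.** The SAP has "patient and therapist SoCT total scores) assessed at baseline prior to randomization", while the protocol says "After completion of the baseline assessment, study participants will have an appointment set up to meet with one of" the trained therapists. The treating therapist therefore appears not yet to have met the patient when that score is due.

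**The concern.** Patients of the same therapist may resemble each other, because therapists differ in results and, for therapist SoCT, in how leniently they score. A model with no therapist term treats those patients as independent apart from site. The consequence depends on how therapists are spread over arms:

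- Similar proportions of both arms per therapist: the therapist differences are noise that the analysis could remove, so precision is lost.
- Assignment that leans by arm: therapist differences leak into the arm contrast and the test becomes too liberal.
- Each therapist in one arm only: the problem is serious.

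Baseline adjustment may not help. If the treating therapist does not supply the baseline score, that score carries none of the therapist's level.

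Separately, the app effect itself could vary between therapists, since the protocol refers to "therapists who access or need to assign HW based upon contents of the app CBTMobileWork-V". The documents give no size for this.

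**Working it through.** **Inputs from the documents.** d = 0.50, testwise alpha .01, power .80, 96 per group analysed, 134 per group enrolled, 28% attrition, ten therapists. Equal caseloads would give 268/10 = 26.8 randomized and 192/10 = 19.2 analysed per therapist. **Assumed:** therapist share of outcome variance (ICC) .01 to .20; SD of the app effect across therapists (τ) .2 to .4 outcome SDs.

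**1. The plan's own figure.** SE = √(2/96) = 0.1443 SD. A two-sided noncentral t test with 190 df gives power .8045, and 96/(1 − .28) rounds up to 134. Both stated figures reproduce. No therapist effect enters them.

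**2. Therapists treat both arms equally and differ in level only.** Adjusting for therapist multiplies the SE by √(1 − ICC).

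| ICC | SE factor | 99% half-width (SD) | Power at d = 0.50 |
|---|---|---|---|
| 0 (plan) | 1 | .376 | .805 |
| .01 | .995 | .374 | .809 |
| .05 | .975 | .366 | .828 |
| .10 | .949 | .356 | .852 |
| .20 | .894 | .336 | .897 |

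This compares the adjusted analysis with the stated calculation. Simulation of the same trial analysed both ways (192 patients, ten therapists, one time point, complete data, fixed site, 20,000 runs per setting, no baseline term) gives power without and with the intercept of .811 and .825, .829 and .856, and .840 and .897 at shares .05, .10 and .20. The gain from the term itself is thus about 1 to 6 points. Type I error of the planned test over these settings is .004 to .011.

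**3. Baseline adjustment (r = .5 assumed).** If baseline carries no therapist level, the gain is 1 to 5 points. If the same therapist rated baseline, it is 0.2 to 0.6 points.

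**4. Assignment leans by arm.** With each therapist's app-arm probability between .30 and .70, planned type I error is about .013 to .024 and returns to about .01 once therapist is adjusted for. A separate run with the same range gave .012/.016/.022 at shares .05/.10/.20. Under a stronger assumed skew (extreme therapists at about e⁻¹/(e⁻¹ + e¹) = 12% and 88% app patients), it is .026 at ICC .05 and .040 at ICC .10. The intercept brings these to .014 and .011, with SEs 5 to 7% larger.

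**5. Therapists nested in arm.** Design effect = 1 + (19.2 − 1) × ICC = 1.18, 1.91, 2.82 at ICC .01, .05, .10. Type I error = 2·P(Z > 2.576/√DEFF) = .018, .062, .125.

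**6. App effect varies by therapist.** With 9.6 patients per therapist and arm, the variance ratio is 1 + τ²/(2/9.6) = 1.192, 1.432, 1.768 at τ = .2, .3, .4. Power of the therapist-by-arm F test on (9, 172) df at .05 is .11, .21, .37. For inference beyond these therapists, planned type I error at τ = .3 is 2·P(Z > 2.576/√1.432) = .031. In simulation (share .05, arms balanced) it is .027 without the intercept and .033 with it.

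**7. Form of the term.** If baseline is one of the modelled responses and carries no therapist level, an intercept constant over time is misspecified. In a three-time-point simulation (balanced arms, 400 runs per setting), the estimated therapist variance was about half the true value, and the SE of the 12-week contrast fell only 1.1/2.1/3.9% at shares .05/.10/.20.

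**The case against.** The strongest reply is that nothing is invalid in the case the documents best support. All therapists are trained on the app, therapy is otherwise identical, and patients are randomized individually, so the planned test holds its level or is conservative. A reader might infer that leaving out therapist makes the primary p-values too small. The documents do not support that unless assignment leans by arm or therapists are nested in arm, and they indicate neither. This part of the reply stands.

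It is also true that the size of the gain rests on variance shares with no source in the documents, that at a share of .01 the gain is negligible, and that most simulated figures come from one time point with complete data and a fixed site term, which is not exactly the planned repeated-measures model.

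A further reply is that optional covariates, residual checks and robust procedures already allow a therapist term. They permit it without naming it, which leaves the choice until after the data are seen. Prespecification is meant to avoid that.

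Two other readings go too far. One is that a therapist term always tightens the intervals. That also requires arms spread similarly within therapist; where assignment leans, intervals can widen, and rightly so. The other is that a therapist-by-arm analysis would show whether the app effect differs by therapist. With power of .11 to .37 at .05, it would not.

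**Conclusion.** The point holds as a cheap improvement, not as an error that undermines the primary analysis. The plan has ten identified therapists, one per patient, a therapist-rated primary outcome, and no therapist term in the SoCT or PHQ-9 models.

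If therapists treat both arms in similar proportions, the cost of the omission is modest precision, and less still if baseline already carries the therapist's level. If assignment leans by arm, the cost is a test that is too liberal, about .013 to .024 and up to .04 under the stronger skew, and the term corrects it. The documents do not settle which case applies, although they lean towards the first. All variance shares, lean patterns and app-effect SDs are assumptions, and caseloads are taken as equal or nearly so except in the skewed runs.

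**What to change.** Record therapist ID for every patient. State in the protocol whether each therapist treats both arms, how patients are assigned to therapists, and who gives the baseline therapist SoCT score. Add to the SAP:

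> All primary models (patient SoCT, therapist SoCT, PHQ-9) include a random intercept for therapist within site, applied to the post-treatment responses with baseline as a covariate. If baseline is modelled as a response, the therapist effect is allowed to differ between baseline and follow-up.

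The planned site term can stay as it is.

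As a descriptive sensitivity analysis, add a random therapist-by-arm term and report the arm contrast with its 99% interval and the therapist-by-arm variance with its interval. Attach no pass/fail label, and state that with ten therapists this can neither establish nor rule out variation by therapist. It is also imprecise for the arm contrast. Approximated by a t test on ten within-therapist differences (9 df), the 99% half-width is .44 SD against .37 planned (share .05, no baseline term, balanced arms).

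If therapists prove to be nested in arm, test the arm contrast against between-therapist variation.

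The cost is one recorded variable and a few sentences. One downside should be stated: the intercept alone slightly raises type I error for inference beyond these therapists if the app effect varies between them, for example from .027 to .033 at an SD of .3.

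### The plan does not say how baseline PHQ-9 enters the primary depression model; one form, using baseline once, should be named in advance

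*Combined protocol and SAP*

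**What the plan says.** The Analysis Plan for Aims 2a and 2b will "fit linear mixed models for the primary distal outcome of depressive symptoms at baseline prior to randomization, 12-weeks post-therapy initiation, and 6-months post-treatment". The hypotheses are tested thus: "group comparisons between treatment groups will be performed at a) 12-weeks post-therapy initiation (Hypothesis 2a) and b) 6-months post-therapy (Hypothesis 2b". The section names no baseline PHQ-9 covariate and no constraint that the arms share a baseline mean. For the rest of the model it points to Aim 1, while saying that the match is not complete.

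The Analysis Plan for Primary Aim 1 has arm, categorical time and their interaction, and counts baseline among the assessment times. On covariates it says: "In addition to the baseline value of the SoCT total scores, time-invariant and/or time-dependent covariates may be included". The only baseline score named there is the SoCT.

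Preliminary Analyses adds: "Covariates/confounders will be included in analyses secondarily and their impact on the results will be evaluated".

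The Sample Size Justification plans the PHQ-9 comparison as "at least a 2.0-point difference in treatment group means assuming a SD of 4.00", using a post-therapy SD and no baseline correlation. Under Data Analysis, "the level of statistical significance will be set conservatively at .01 to limit type 1 error inflation".

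**The concern.** PHQ-9 is a primary outcome, every participant should have a pre-randomization value, and the text allows at least two models. One leaves baseline unused for adjustment when data are complete, so the 99% intervals are wider than they need be. The other uses baseline both as response and as predictor, which can make the reported standard error too small in a trial that chose .01 to control type 1 error. Two analysts following the text could report different intervals and p-values, and the choice could be made after the data are seen.

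**Working it through.** **Inputs from the Sample Size Justification.** Difference 2.0 points, SD 4.0 (d = 0.50), testwise alpha .01, power .80, 96 evaluable and 134 enrolled per arm, attrition 20% at 12 weeks and 28% at 6 months. Sidedness is not stated.

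**Assumed.** The baseline-to-follow-up correlation rho is not in the documents; .2 to .7 is used. It is taken as equal at both follow-up visits, the SD as 4 at every visit, the correlation between the two follow-up visits as the larger of rho and .5, and dropout as completely at random.

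**1. The plan's own figures.** The normal formula gives n = 2(2.576 + 0.842)²/0.50² = 93.4, so 94 per arm. The two-sided noncentral t gives 96, with power .805. One-sided versions give 81 or 82 and do not match. 96/(1 − 0.28) = 133.3, so 134. The figures reproduce as an unadjusted two-sided comparison.

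**2. Complete data, 96 per arm.** With arm, time, arm-by-time and free baseline means, the follow-up contrast has SE = 4√(2/96) = 0.577 at any rho. That is the raw difference in means. With a common baseline mean, SE = 0.577 × √(1 − rho²):

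- rho .3: 0.577 × 0.954 = 0.551
- rho .5: 0.577 × 0.866 = 0.500
- rho .7: 0.577 × 0.714 = 0.412

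At rho .5 the 99% half-width falls from 2.602 × 0.577 = 1.50 to 2.602 × 0.500 = 1.30 points.

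**3. Planned dropout.** 134 × 0.80 = 107 per arm at 12 weeks and 134 × 0.72 = 96 at 6 months. Generalized least squares information was summed over the three dropout patterns, and power = Φ(2.0/SE − 2.576):

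| rho | 12 weeks, free → common | gain (points) | 6 months, free → common | gain (points) |
|---|---|---|---|---|
| .2 | .864 → .876 | 1.2 | .829 → .842 | 1.3 |
| .3 | .868 → .896 | 2.8 | .833 → .863 | 3.0 |
| .5 | .880 → .950 | 7.0 | .850 → .926 | 7.6 |
| .7 | .899 → .995 | 9.6 | .880 → .990 | 11.0 |

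**4. Baseline used twice.** Suppose baseline PHQ-9 is a covariate with one slope while the baseline row stays in the response, under compound symmetry with one common variance. The baseline row has slope 1 on itself, so the fitted slope is b = (1 + 2rho)/3. The residual variance is 16(1 − b)² at baseline and 16(1 − 2b·rho + b²) at follow-up. The model reports one averaged variance.

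At rho .5:

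- b = 0.667.
- Baseline residual variance: 16 × 0.111 = 1.78. Follow-up: 16 × 0.778 = 12.44.
- Average: (1.78 + 2 × 12.44)/3 = 8.89.
- Reported SE: √(8.89 × 2/96) = 0.430. Actual SE: √(12.44 × 2/96) = 0.509.
- The nominal 2.576 cut-off is really 2.576 × 0.430/0.509 = 2.18, a two-sided level of about .029.

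The same arithmetic gives about .025, .027 and .032 at rho .2, .3 and .7. Simulation under the null (96 per arm, complete data, compound symmetry, 8,000 trials per setting) gave .024 to .025 at rho .2, .026 at .3, .029 at .5 and .032 to .033 at .7.

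**The case against.** The strongest reply is that the PHQ-9 section does not set out a free-standing model. It adopts the Aim 1 approach, and that approach names the baseline value of its own outcome. Read in parallel, baseline PHQ-9 would be a covariate. The sentence that makes covariates secondary follows a screening step for suspected confounders and may not be meant for the outcome's own baseline. This stands as far as it goes. A reader might infer that the 2a and 2b contrasts are definitely plain differences in post-treatment means, and the documents do not support that as fact. But the parallel reading is never written, the borrowing is qualified, and followed literally it leads to the double use in step 4.

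It also stands that likelihood estimation with dropout already draws on baseline data from those who leave. At rho .5 the free-baseline SEs are 0.533 and 0.554, against raw values of 4√(2/107) = 0.547 and 0.577. So baseline is not wholly unused. The free-baseline model exceeds .80 power throughout the table, an unadjusted randomized contrast is unbiased, and its interval allows for chance imbalance.

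Finally, the gain depends on a correlation that the documents lack. At rho .2 it is about 1 point. Equal correlation at both visits may flatter the 6-month figures.

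**Conclusion.** The point holds as a gap in specification with a nearly free gain in efficiency. The plan leaves the role of baseline PHQ-9 open. The free-baseline reading costs about 1 to 11 power points over rho .2 to .7 under the planned dropout. The carry-over reading can raise the true level of a nominal .01 test to about .025 to .033. That second figure belongs to a compound-symmetry, single-slope fit with complete data. The plan leaves the covariance structure to fit indices, so it shows what can happen and is not a forecast.

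Two stronger inferences should be resisted. The sample size is not wrong: 96 and 134 per arm reproduce, and .80 power is met without adjustment. Nor is the unadjusted contrast biased.

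**What to change.** In the Analysis Plan for Aims 2a and 2b, state that the primary PHQ-9 model adjusts for baseline PHQ-9, that it does so in the primary analysis, and that baseline is used once. Name one of these in advance:

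- the three-visit mixed model with a common baseline mean across arms (no arm effect at the pre-randomization visit) and an unstructured covariance; or
- a mixed model of the 12-week and 6-month rows only, with baseline PHQ-9 and baseline-by-time as covariates.

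Take the 2a and 2b contrasts from that model. State that the secondary status of covariates under Preliminary Analyses does not apply to baseline PHQ-9. Keep N at 268 and treat the gain as margin, because the correlation is unknown.

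The cost is one or two sentences, with no new data, visits or participants. The three-visit form also keeps every randomized participant who has any PHQ-9 value.
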